12.3 Common Serious Adverse Events

Not applicable

12.4 ECOG Performance Status Scale

ECOG PERFORMANCE STATUS*		
Grade	ECOG	
0	Fully active, able to carry on all pre-disease performance without restriction	
1	Restricted in physically strenuous activity but ambulatory and able to carry out work of a light or sedentary nature, e.g., light house work, office work	
2	Ambulatory and capable of all selfcare but unable to carry out any work activities. Up and about more than 50% of waking hours	
3	Capable of only limited selfcare, confined to bed or chair more than 50% of waking hours	
4	Completely disabled. Cannot carry on any selfcare. Totally confined to bed or chair	
5	Dead	

Reference

(GPF v.6.0)

ECOG	Eastern Cooperative Oncology Group	
FAS	Full Analysis Set	
Hb	Hemoglobin	
HLGT	High Level Group Term	
HLT	High Level Term	
ICH	International Council for Harmonisation	
IHD	Ischemic Heart Disease	
ISN	International Study Number	
mCRPC	Metastatic Castration-Resistant Prostate Cancer	
MedDRA	Medical Dictionary for Regulatory Activities	
NA	Not Applicable	
NCI	National Cancer Institute	
PD	Pharmacodynamics	
РК	Pharmacokinetics	
PRES	Posterior Reversible Encephalopathy Syndrome	
PSA	Prostate-Specific Antigen	
РТ	Preferred Term	
SAF	Safety Analysis Set	
SAP	Statistical Analysis Plan	
SCAR	Severe Cutaneous Adverse Reactions	
SD	Standard Deviation	
SMQ	Standardized MedDRA Queries	
SOC	System Organ Class	
SPM	Second Primary Malignancies	
TEAE	Treatment Emergent Adverse Event	
TLFs	Tables, Listings, and Figures	
ULN	Upper limit of normal	
WHO	World Health Organization	
WHODDE(B2)	WHO Drug Dictionary Enhanced (B-2 Format)	

List of Key Terms

Terms	Definition of terms
Baseline	Assessments of subjects as they enter a trial before they receive any treatment.
Endpoint	Variable that pertains to the efficacy or safety evaluations of a trial.
Enroll	To register or enter a subject into a clinical trial. NOTE: Once a subject has received the study drug or placebo, the clinical trial protocol applies to the subject.
Investigational period	Period of time where major interests of protocol objectives are observed, and where the test drug or comparative drug (sometimes without randomization) is usually given to a subject, and continues until the last assessment after completing administration of the test drug or comparative drug.
Post investigational period	Period of time after the last assessment of the protocol. Follow-up observations for sustained adverse events and/or survival are done in this period.
Screening	A process of active consideration of potential subjects for enrollment in a trial.
Screen failure	Potential subject who did not meet 1 or more criteria required for participation in a trial.
Screening period	Period of time before entering the investigational period, usually from the time when a subject signs the consent until just before the test drug or comparative drug (sometimes without randomization) is given to a subject.
Study period	Period of time from the first site initiation date to the last site completing the study.
Variable	Any entity that varies; any attribute, phenomenon or event that can have different qualitative or quantitative values.

1 INTRODUCTION

This Statistical Analysis Plan (SAP) contains a more technical and detailed elaboration of the principal features of the analysis described in the protocol, and includes detailed procedures for executing the statistical analysis of the primary and secondary endpoints and other data.

The SAP is finalized and signed prior to database hard lock.

This statistical analysis is coordinated by the responsible biostatistician of Data Science, API. Any changes from the analyses planned in the SAP will be justified in the Clinical Study Report (CSR).

2 FLOW CHART AND VISIT SCHEDULE

Refer to Section V. FLOW CHART AND SCHEDULE OF ASSESSMENTS of the protocol.

3 STUDY OBJECTIVE(S) AND DESIGN

3.1 Study Objective(s)

The objective is to evaluate the safety and efficacy of enzalutamide in Indian patients with progressive mCRPC previously treated with docetaxel-based chemotherapy as per locally approved prescribing information.

3.1.1 Primary Objective

To evaluate the safety and tolerability of enzalutamide in Indian patients with progressive mCRPC previously treated with docetaxel-based chemotherapy.

3.1.2 Secondary Objective

To evaluate the effect of enzalutamide on PSA.

3.2 Study Design

This study is a multicenter phase 4, open-label, single-arm, safety and efficacy study of enzalutamide (160 mg/day) in patients with progressive mCRPC who have previously been treated with docetaxel-based chemotherapy. Approximately 50 patients will be enrolled and treated with enzalutamide 160 mg once daily until study discontinuation criteria is met.

Safety and tolerability will be assessed by the collection of adverse events, vital signs, physical examinations and safety laboratory evaluations.

PSA will be collected for assessment of prostate cancer status on Screening Visit, Days 1, 29, 57, 85, 169, every subsequent 84 days and Safety Follow-up Visit.

Subjects will have a safety follow-up visit 30 days after their last dose of study drug or prior to initiation of another investigational agent or new therapy including commercial enzalutamide for prostate cancer, whichever occurs first.

3.3 Randomization

Randomization will be not performed as this is single-arm study.

4 SAMPLE SIZE

The sample size of 50 subjects is not based on a statistical power calculation.

5 ANALYSIS SETS

In accordance with International Conference on Harmonization (ICH) recommendations in guidelines E3 and E9, the following analysis sets will be used for the analyses.

Detailed criteria for analysis sets will be laid out in Classification Specifications and the allocation of subjects to analysis sets will be determined prior to database hard-lock.

5.1 Full Analysis Set (FAS)

The FAS will consist of all subjects who received at least one dose of study drug and have at least one post baseline measurement. This will be the primary analysis set for efficacy analyses.

5.2 Safety Analysis Set (SAF)

The SAF consists of all subjects who took at least 1 dose of study drug, and will be used for safety analyses.

For the statistical summary of the safety data, the SAF will be used.

6 ANALYSIS VARIABLES

6.1 Efficacy Endpoints

Secondary endpoints

• Confirmed PSA response rate (≥ 50% decline in PSA from baseline to the lowest postbaseline PSA result, with a consecutive assessment conducted at least 3 weeks later to confirm the PSA response)

6.2 Safety Variables

Primary endpoints

- Nature, frequency and severity of adverse events
- Safety laboratory tests: biochemistry and hematology
- Physical examination
- Vital signs (blood pressure, pulse and temperature)

Other endpoints

• Weight

TEAE (Treatment Emergent Adverse Event) is defined as an adverse event observed after starting administration of the study drug.

A drug-related TEAE is defined as any TEAE with a causal relationship of YES by the investigator or with missing assessment of the causal relationship.

AESI Category	Selection based on MedDRA 26.0	
Convulsions (Seizure)	Narrow SMQ of 'Convulsions'.	
Hypertension	Narrow SMQ 'Hypertension'.	
Neutrophil Count Decreased	PTs of 'Neutrophil Count Decreased', 'Neutropenia', 'Agranulocytosis',' Granulocyte Count Decreased', 'Granulocytopenia', 'Febrile Neutropenia', 'Neutrophil Percentage Decreased', 'Band Neutrophil Count Decreased', 'Band Neutrophil Percentage Decreased', 'Neutropenic Sepsis', 'Neutropenic Infection' And 'Neutrophil Count Abnormal'.	
Cognitive and Memory Impairment	All PTs under the MedDRA HGLT: 'Mental Impairment Disorders'.	
Ischemic Heart Disease (IHD)	Narrow SMQs of 'Myocardial Infarction' And 'Other Ischemic Heart Disease'.	
Other Selected Cardiovascular Events		
Posterior Reversible	PT of 'Posterior Reversible Encephalopathy Syndrome'.	
Encephalopathy Syndrome (PRES)		
Fatigue	PTs of 'Fatigue', 'Asthenia'.	
Renal Disorder	Broad ^[1] SMQ of 'Acute Renal Failure'. Narrow SMQs of 'Malignant Or Unspecified Tumours'	
Second Primary Malignancies (SPM) ^[2]	Customized To Exclude PTs of 'Congenital Fibrosarcoma', 'Congenital Malignant Neoplasm', 'Congenital Retinoblastoma', 'Metastases To…', 'Metastasis', 'Metastatic Neoplasm', 'Prostate Cancer…', 'Carcinoid Tumour of The Prostate', And 'Neoplasm Prostate' And (Inclusive of) Narrow SMQ of 'Myelodysplastic Syndrome', And (inclusive of) All PTs under HLT of 'Myeloproliferative Disorders (Excl Leukaemias)' Note: Non-Melanoma Skin Cancers Are Excluded (Preferred Terms Of 'Basal Cell Carcinoma', 'Basosquamous Carcinoma', 'Basosquamous Carcinoma Of Skin', 'Keratoacanthoma', 'Skin Cancer', 'Skin Cancer Metastatic' 'Squamous Cell Carcinoma', 'Bowen's disease').	
Fall	PT of 'Fall'.	
Fractures All PTs under the MedDRA HGLT: 'Fractures' An And Joint Injuries'.		
Loss of Consciousness	PTs of 'Loss of Consciousness', 'Syncope', 'Presyncope'.	
Thrombocytopenia Musculoskeletal Events	 PTs of 'Thrombocytopenia', 'Platelet Count Decreased'. PTs of 'Back Pain', 'Arthralgia', 'Myalgia', 'Musculoskeletal Pain', 'Pain In Extremity', 'Musculoskeletal Stiffness', 'Muscular Weakness','Muscle Spasms'. 	
Severe Cutaneous Adverse Reactions (SCAR)	Narrow SMQ of 'Severe Cutaneous Adverse Reactions'.	

AESI (Adverse Events of Special Interest) are defined as below.

AESI Category	Selection based on MedDRA 26.0	
Angioedema	Narrow SMQ of 'Angioedema'.	
	PTs of 'Butterfly rash', 'Exfoliative rash', 'Eyelid rash',	
	'Genital rash', 'Heliotrope rash', 'Mucocutaneous rash',	
	'Nodular rash', 'Paraneoplastic rash', 'Penile rash', 'Perineal	
	rash', 'Rash', 'Rash erythematous', 'Rash follicular', 'Rash	
Rash	macular', 'Rash maculo-papular', 'Rash maculovesicular',	
Kasii	'Rash morbiliform', 'Rash neonatal', Rash papular', 'Rash	
	papulosquamus', 'Rash pruritic', 'Rash pustular', 'Rash	
	rubelliform', 'Rash scarlataniniform',' Rash vesicular', 'Septic	
	rash', 'Systemic lupus erythematosus rash', 'Vasculitic rash',	
	'Viral rash', 'Vulvovaginal rash'.	
	Narrow SMQ of 'Hepatic Failure, Fibrosis And Cirrhosis	
Δ	And Other Liver Damage Related Conditions', 'Hepatitis,	
Hepatic Disorder	Non-Infectious' And 'Liver Related Investigations, Signs	
	And Symptoms'.	

SMQ: Standardized MedDRA Query, HLT: High Level Term, HLGT: High Level Group Term.

[1] Broad includes either broad or narrow.

[2] AE terms identified as second primary malignancies according to the search criteria undergo review to confirm.

6.3 Other Variables

• Duration of exposure

For each subject, the length of time on treatment will be calculated in days, using the following formula:

- Last dose date of enzalutamide First dose date of enzalutamide + 1, for patients who completed.
- Discontinuation dose date of enzalutamide First dose date of enzalutamide + 1, for patients who discontinued.
- Percent overall compliance
 - Percent compliance = Number of taken capsules of enzalutamide / Number of planned capsules of enzalutamide x 100 (%)
 - Number of taken capsules of enzalutamide = Sum of (Number of prescribed capsules of enzalutamide Number of returned capsules of enzalutamide)
 - Number of planned capsules of enzalutamide = Sum of ((Stop Date Start Date + 1) x Dose / 40).
- Duration of disease at screening (month)
 - Duration of disease at screening (month) = (Date of screening visit Date of histological or cytological diagnosis of prostate cancer + 1) / 30.

If the onset day and/or month of diagnosis is unknown, then the day and/or month will be imputed by 1st and January respectively.

- Duration of metastatic progression at screening (month)
 - Duration of metastatic progression at screening (month) = (Date of screening visit First Date of Diagnosis of Metastatic Progression + 1) / 30.

If the onset day and/or month of diagnosis is unknown, then the day and/or month will be imputed by 1st and January respectively.

7 STATISTICAL METHODOLOGY

7.1 General Considerations

- All data processing, summarization, and analyses will be performed using SAS® Version 9.4 or higher on Red Hat Enterprise Linux.
- For continuous variables, descriptive statistics will include the number of subjects (n), mean, standard deviation (SD), median, minimum, and maximum.
- For categorical variables: number and percentages of subjects will be described.
- Specifications for table, figures, and data listing formats can be found in the TLFs specifications for this study.
- MedDRA will be used as the coding dictionary for adverse event and medical history.
- WHODDE(B2) will be used as the coding dictionary for previous and concomitant medications.
- Baseline is defined as last nonmissing value before the first dose of the study drug.
- Change from baseline to postbaseline will be calculated as: postbaseline value baseline value. If the baseline value is missing, then that subject is not included in the calculation at any visit.

7.2 Study Population

7.2.1 Disposition of Subjects

The following subject data will be summarized and presented with regard to all subjects with Screening Failure Log and Case Report Form:

- Number of subjects with informed consent
- Number of subjects who discontinued before registration
- Number of subjects who registered

The following subject data will be summarized and presented with regard to subjects with informed consent:

- Number and percentage of subjects who prematurely discontinued during the screening period
- Number and percentage of subjects who prematurely discontinued during the screening period by primary reason for withdrawal

The following subject data will be summarized and presented with regard to all registered subjects:

- Number and percentage of subjects who prematurely discontinued during the study period
- Number and percentage of subjects who prematurely discontinued during the study period by primary reason for withdrawal
- Number and percentage of subjects who took study drug
- Number and percentage of subjects who were included/excluded in SAF and FAS

The following subject data will be summarized and presented with regard to subjects who took the study drug:

• Number and percentage of subjects who were excluded from SAF and FAS by reason

7.2.2 **Protocol Deviations**

Protocol deviations as defined in the study protocol (Section 8.1.6 Protocol Deviations) will be assessed for all subjects allocated to treatment. The number and percentage of subjects meeting any criteria will be summarized for each criterion and overall, by total as well as by study site. Subjects deviating from a criterion more than once will be counted once for the corresponding criterion. Any subjects who have more than one protocol deviation will be counted once in the overall summary. A data listing will be provided by site and subject.

The protocol deviation criteria will be uniquely identified in the summary table and listing. The unique identifiers will be as follows:

- PD1 Entered into the study even though they did not satisfy entry criteria,
- PD2 Developed withdrawal criteria during the study and was not withdrawn,

PD3 - Received wrong treatment or incorrect dose,

PD4 - Received excluded concomitant treatment.

7.2.3 Demographic and Other Baseline Characteristics

Demographic and other baseline characteristics will be summarized by descriptive statistics or categorical analysis for SAF and FAS.

The following demographic variables will be summarized and presented.

Item	Classification	Analysis Methods
Age [at the time of informed	Measurement value	Descriptive statistics
consent] (years)	<75,>=75	Categorical analysis
	<65, 65 to <75, >=75	
EudraCT Age Category	$>=18$ years to $\leq=64$ years,	Categorical analysis
	>=65 years to <=84 years,	
	>=85 years	
Sex	Male, Female	Categorical analysis
Self-Reported Race	White, Black or African American,	Categorical analysis
_	American Indian or Alaska Native,	
	Asian Indian, Chinese, Filipino,	
	Japanese, Korean, Vietnamese,	
	Other Asian, Native Hawaiian,	
	Guamanian or Chamorro, Samoan,	
	Other Pacific Islander	
Ethnicity	Not Hispanic or Latino, Hispanic or	Categorical analysis
	Latino	
Height [Screening] (cm)	Measurement value	Descriptive statistics
Weight [Screening] (kg)	Measurement value	Descriptive statistics
Weight[Day 1] (kg)	Measurement value	Descriptive statistics

Item	Classification	Analysis Methods
BMI [Screening] (kg/m^2)	BMI (kg/m ²) = Weight (kg) / (Height (cm) / 100) ²	Descriptive statistics
BSA [Screening] (m ²)	$BSA (m^{2}) = Weight (kg)^{0.425} x Height (cm)^{0.725} x 0.007184$	Descriptive statistics
ECOG Performance Status	Grade 0, Grade 1, Grade 2, Grade 3, Grade 4, Grade 5	Categorical analysis
Previous Disease	No, Yes	Categorical analysis
Concomitant Disease	No, Yes	Categorical analysis
Duration of disease at screening	Measurement value	Descriptive statistics
(month)	<60month, >=60month <=Median, >Median	Categorical analysis
Primary Gleason score initial histological/cytological diagnosis	1, 2, 3, 4, 5, Unknown	Categorical analysis
Secondary Gleason score initial histological/cytological diagnosis	1, 2, 3, 4, 5, Unknown	Categorical analysis
Total Gleason score initial histological/cytological diagnosis	1, 2, 3, 4, 5, 6, 7, 8, 9, 10, Unknown Low: 1-4, Medium: 5-7, High: 8-10	Categorical analysis
Clinical Tumor Stage (T) initial histological/cytological diagnosis	TX, T0, T1, T2, T3, T4, Unknown	Categorical analysis
Pathologic Tumor Stage (pT) initial histological/cytological diagnosis	pT2, pT3, pT4, Unknown	Categorical analysis
Clinical Lymph Node (N) Stage initial histological/cytological diagnosis	NX, N0, N1, Unknown	Categorical analysis
Pathological Lymph Node (pN) Stage initial histological/cytological diagnosis	pNX, pN0, pN1, Unknown	Categorical analysis
Distant Metastasis (M) initial histological/cytological diagnosis	MX, M0, M1, Unknown	Categorical analysis
Duration of metastatic progression at screening (month)	Measurement value	Descriptive statistics
Location	Abdominal cavity, Adrenal gland, Anus, Bile duct, Bladder, Body, Bone, Bone marrow, Brain, Breast, Cervix uteri, Chest, Colon, Esophagus, Gallbladder, Head, Heart, Head and neck, Kidney, Liver, Lung, Lymph node, Mediastinum, Neck, Omentum, Oral cavity, Pancreas, Pelvis, Penis, Pericardium, Peritoneum, Pleura, Prostate gland, Rectum, Retroperitoneum, Skin, Small intestine, Spleen, Stomach, Testis, Other	Categorical analysis
Prostate Cancer Treatment History - Radiation	No, Yes	Categorical analysis

Item	Classification	Analysis Methods
Prostate Cancer Treatment History	No, Yes	Categorical analysis
- Procedure		
Prostate Cancer Treatment History	No, Yes	Categorical analysis
- Drug Therapy		
PSA at Baseline	Measurement value	Descriptive statistics
	<2 ug/L, >=2 ug/L	Categorical statistics
	<=Median, >Median	
Hb at Baseline	Measurement value	Descriptive statistics
	<=Median, >Median	Categorical analysis
ALP at Baseline	Measurement value	Descriptive statistics
	<=Median, >Median	Categorical analysis
Alb at Baseline	Measurement value	Descriptive statistics
	<=Median, >Median	Categorical analysis

7.2.4 Previous and Concomitant Medications

Previous Medications/Non-Medication Therapy mean drugs and therapies undergone before entering the investigational period and Concomitant Medications/ Non-Medication Therapy refer to drugs and therapies used during the investigational period.

Previous and Concomitant Medications/Non-Medication Therapy will be summarized for SAF and FAS.

Previous and Concomitant Medications/Non-Medication Therapy and Analysis Methods

Item	Classification	Analysis Methods
Previous Medications	No, Yes	Categorical analysis
Previous Non-Medication Therapy	No, Yes	Categorical analysis
Concomitant Medications	No, Yes	Categorical analysis
Concomitant Non-Medication Therapy	No, Yes	Categorical analysis

7.3 Study Drugs

7.3.1 Exposure

Analysis set: FAS, SAF

Duration of exposure will be summarized using descriptive statistics.

7.3.2 Treatment Compliance

Analysis set: FAS, SAF

Percent overall compliance will be summarized using descriptive statistics.

7.4 Analysis of Efficacy

Efficacy analysis will be conducted on the FAS.

PSA response rate (the proportion of patients with $\geq 50\%$ decline in PSA from baseline) will be summarized at each visit (See Section 7.11.3).

Confirmed PSA response rate (the proportion of patients with $\geq 50\%$ decline in PSA from baseline to the lowest postbaseline PSA result, with a consecutive assessment conducted at least 3 weeks later to confirm the PSA response) will be summarized.

Summary statistics of measured values and the percent changes from baseline will be calculated at each visit and mean \pm standard deviation (SD) plots will be constructed.

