5.1.3.2 Prohibited Concomitant Treatment

A list of excluded concomitant medications is provided in [Appendix 12.1 List of Excluded Concomitant Medications]. The following medications are prohibited within 4 weeks of day 1 and during the study treatment period:

- 5 α-reductase inhibitors (finasteride, dutasteride);
- Estrogens;
- Cyproterone acetate;
- Abiraterone
- Biologic or other agents with antitumor activity against prostate cancer (with the exception of those therapies identified in inclusion/exclusion criteria);

- Systemic glucocorticoids greater than the equivalent of 10 mg per day of prednisone intended for the treatment of prostate cancer;
- Herbal medications that have known hormonal antiprostate cancer activity and/or are known to decrease PSA levels (i.e., saw palmetto);
- Androgens (testosterone, dehydroepiandrosterone, etc.);
- Investigational agents.

In addition, bisphosphonates and denosumab are prohibited unless stabilized for 2 weeks prior to day 1 and held constant throughout study treatment or administered for diagnosis of osteoporosis.

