5.1.3.4 Permitted Concomitant Treatment

The following treatments are allowed during the study (and do not require study drug discontinuation) including, but not limited to:

- Blood transfusions and growth factor support per SOC and institutional guidelines;
- Steroid use (for indication other than prostate cancer) per SOC;

- Pain therapy per SOC and institutional guidelines;
- Palliative radiation therapy including external beam radiotherapy or systemic radionuclides (e.g., Samarium or Strontium);
- Vaccine therapy that has prior market authorization and is not intended to treat prostate cancer;
- Palliative surgical procedures to treat skeletal-related events.

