5.3 Efficacy and Pharmacokinetics Assessments

5.3.1 Efficacy Assessments

PSA response \geq 50% is defined as \geq 50% reductions in PSA level from baseline to the lowest post-baseline PSA result as determined by the central laboratory, with a consecutive assessment conducted at least 3 weeks later to confirm the PSA response.

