6 DISCONTINUATION

6.1 **Discontinuation of Individual Subject(s)**

The subject is free to withdraw from the study treatment and/or study for any reason and at any time without giving reason for doing so and without penalty or prejudice. The Investigator is also free to terminate a subject's involvement in the study at any time if the subject's clinical condition warrants it.

Discontinuation Criteria from Study Drug Treatment for Individual Subjects:

- Any AE that is intolerable to the subject which cannot be ameliorated by the use of adequate medical intervention and/or dose reduction or that in the opinion of the Investigator would lead to undue risk to the subject if dosing is continued.
- Subject who experiences a seizure or any condition that significantly predisposes the subject to seizure such as brain metastasis or clinically evident stroke.
- Subject who experiences a confirmed event of PRES by brain imaging, preferably by MRI.
- Subject initiates an investigational agent or new therapy for prostate cancer.
- Subject who has evidence of radiological disease progression and/or PSA progression as confirmed by the Investigator and is no longer deriving clinical benefit. Imaging test can be done at the discretion of the investigator and are not part of the study.
- Subject has discontinued ADT (GnRH agonist/antagonist) and has a testosterone value in the noncastrate range (> 50 ng/dL).
- Subject who is, in the opinion of the Investigator or the Medical Monitor, non-compliant with the protocol requirements.
- Subject is lost to follow-up despite reasonable efforts by the Investigator to locate the subject.
- Subject withdraws consent for the study.

Subject will be discontinued from the 30 day study follow-up (Safety or Long-term Follow-up) if any of the following occur:

- Subject is lost to follow-up despite reasonable efforts by the Investigator to locate the subject.
- Subject withdraws consent for further follow-up.
- Death.
- Study termination by the Sponsor.

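### The confirmed PSA response rate has no rule for PSA measured after permitted palliative radiotherapy, radionuclides or steroids, so a first 50% fall seen after them counts as an enzalutamide response

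*SAP*

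**What the plan says.** SAP 6.1 and 7.4 define confirmed PSA response as a fall of 50% or more, taken as the "decline in PSA from baseline to the lowest postbaseline PSA result". Both sections then add a timing condition for confirmation, worded "with a consecutive assessment conducted at least 3 weeks later to confirm the PSA response". Protocol 5.3.1 uses the same rule, measuring the fall "from baseline to the lowest post-baseline PSA result as determined by the central laboratory". None of these sections says when the eligible period ends, or how to handle a PSA value taken after another treatment has begun.

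SAP 7.4 also plans a simpler response rate that "will be summarized at each visit (See Section 7.11.3". That section covers PSA. For the Day XXXX visits of discontinued subjects it accepts only values up to the withdrawal day. Safety Follow-up has its own row.

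On co-treatment, protocol 5.1.3.4 allows, without stopping study drug, "Palliative radiation therapy including external beam radiotherapy or systemic radionuclides (e.g., Samarium or Strontium") and steroids given for reasons other than prostate cancer, with no dose limit stated. Protocol 5.1.3.2 prohibits "Systemic glucocorticoids greater than the equivalent of 10 mg per day of prednisone intended for the treatment of prostate cancer". Protocol 6.1 stops study drug when "Subject initiates an investigational agent or new therapy for prostate cancer".

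SAP 7.2.4 says "Previous and Concomitant Medications/Non-Medication Therapy will be summarized for SAF and FAS". The rows are No/Yes, with medication and non-medication therapy kept apart.

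**The concern.** The only efficacy objective is the effect of enzalutamide on PSA, and there is no control arm in which the effect of other treatment would also appear. The protocol limits outside influences on PSA through its prohibited list, but the analysis has no counterpart for the treatments it permits. If one of these lowers PSA in a subject who had not responded to enzalutamide, that subject enters the confirmed rate as a responder. A reader of the study report could not tell from the summary tables how many responses arose this way.

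**Working it through.** **Plan figures.** There is nothing to reproduce. The sample size of 50 is stated not to rest on a power calculation, and the documents give no target rate, test or interval for PSA response.

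**Can a fall after co-treatment count?** Take a hypothetical subject with baseline PSA 100:
- Day 29: 80 (20% fall). Day 57: 75 (25% fall).
- Day 60: a permitted radionuclide is given.
- Day 85: 40 (60% fall). Day 169: 38 (62% fall). Day 253: still at or below 50.

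The lowest value is 38 on Day 169. The next scheduled PSA is 84 days later, which exceeds 21 days, and is still at least 50% below baseline. The subject is a confirmed responder under the text, although the fall was only 25% before the radionuclide.

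**Can a value after last dose create a response?** Safety Follow-up falls 30 ± 7 days after last dose, that is, 23 to 37 days, and is the last scheduled PSA. Protocol Table 1 marks no PSA under the unscheduled visit. A nadir first reached there has no scheduled later value to confirm it, so it would not normally give a confirmed response. It can confirm an earlier fall: if the previous PSA was on or before last dose, the gap is at least 23 days, which meets the 21-day rule. The visit may come sooner if new prostate cancer therapy is about to start.

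**Effect per subject.** One subject changes the rate by 1/n. At n = 50 this is 1/50 = 2.0 percentage points, and slightly more if the FAS is smaller than 50.

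**Illustration on assumed inputs.** Let p be the confirmed response rate without co-treatment, q the share of subjects given a relevant permitted treatment, and f the share of those otherwise non-responding who then show a confirmed 50% fall. None of the three is in the documents.

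Inflation = q × (1 − p) × f

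| Case | q | p | f | Inflation | Subjects of 50 |
|---|---|---|---|---|---|
| Low | 5% | 60% | 10% | 0.05 × 0.40 × 0.10 = 0.2 points | 0.1 |
| Middle | 10% | 40% | 25% | 0.10 × 0.60 × 0.25 = 1.5 points | 0.75 |
| High | 30% | 30% | 50% | 0.30 × 0.70 × 0.50 = 10.5 points | 5.25 |

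For scale, an observed 20/50 (40%) has an exact (Clopper-Pearson) 95% interval of 26.4% to 54.8%, a half-width of about 14 points. The middle case is small beside that; the high case is not.

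**What the planned outputs show.** Required ADT makes the concomitant medication row Yes for any subject on a GnRH agent. The non-medication row is more informative but does not separate radiotherapy from other therapy. Protocol 7.3.2 adds a listing of all medications. Nothing sets these dates against PSA, and SAP 7.8 and 7.9 plan no subgroup or other analyses.

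**The case against.** The strongest reply is that counting PSA outcomes regardless of permitted palliative care is a legitimate choice for a phase 4 study run under the local label, and that the endpoint is secondary and descriptive, with no test or threshold depending on it. Both points stand. They are reasons to leave the main definition alone, but they do not argue against one supplementary rate that shows how far the result depends on that choice.

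Several stronger readings are tempting, and the documents do not support them.
- A reader might infer that PSA response as a whole lacks a cut-off. The by-visit rate does not use the nadir, and its Day XXXX values stop at the withdrawal day. What is missing is a statement of whether that limit also governs the nadir.
- A reader might infer that falls after last dose inflate the confirmed rate. As shown, the follow-up PSA can normally only confirm an earlier fall.
- A reader might infer that low-dose steroid for prostate cancer is permitted. Protocol 5.1.3.4 covers other indications only, and 5.1.3.2 is silent at or below 10 mg/day. This is an ambiguity.
- A reader might infer that the protocol itself says radiotherapy, radionuclides or steroids lower PSA. Its remark about lowering PSA concerns herbal products only.
- A reader might infer that these treatments are invisible in the outputs. The non-medication row and the medication listing give partial sight of them.

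Direction also needs care. Read literally, confirmation must follow the lowest value, so a responder whose last PSA is the lowest may go unconfirmed, which errs downward. A simple cut-off at co-treatment would err downward too: a subject with a 60% fall on Day 29, radiotherapy on Day 50 and confirmation on Day 57 would become a non-responder although the fall came first. The fix has to avoid this.

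**Conclusion.** The point holds for the confirmed PSA response rate. Its definition has no rule for PSA taken after permitted palliative radiotherapy, radionuclides or systemic steroids, so a confirmed 50% fall first seen after them is credited to enzalutamide.

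The bias is possible rather than shown, and its size is unknown. The firm figure is 2 percentage points per affected subject at n = 50. The range of 0.2 to 10.5 points, with 1.5 in the middle case, rests wholly on assumed inputs, including the assumption that these treatments can lower PSA by half. It should not be quoted as an estimate of the inflation. The primary safety objective is not affected. The change is worth making because it bears on the study's only efficacy question and costs little.

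**What to change.** 1. Keep the main definition of confirmed PSA response.
2. State in SAP 7.4 whether the withdrawal-day limit of SAP 7.11.3 applies to the nadir and its confirmation.
3. Add one supplementary confirmed response rate in which the first 50% fall must occur before the first on-study radiotherapy, radionuclide, or newly started or increased systemic glucocorticoid. Use the date of the first 50% fall, not the date of the nadir. A fall seen before that treatment but confirmed only after it should be shown as its own category, not counted as a non-response.
4. Tabulate the number of subjects receiving each of these treatments.
5. Reconcile protocol 5.1.3.2, 5.1.3.4 and 6.1 on whether steroid at or below 10 mg/day prednisone equivalent intended for prostate cancer counts as new therapy. The answer also affects the deviation counts for PD2 and PD4.

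The cost is one extra table and a supplementary rate that may be lower than the main one. SAP 7.11.1 already handles start dates for concomitant medication, non-medication therapy and radiation, so the dates appear to be collected. Two details need settling: whether the partial-date rule applies here, since imputing the first of the month or January can move a treatment start earlier, and whether steroid dose is recorded well enough to identify an increase.
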